7.2 Secondary Assessments

We will use a similar method to quantify the amount of nausea/vomiting each patient experiences (0 = no nausea/vomiting; 1 = mild/tolerable nausea/vomiting not requiring treatment; 2 = severe/intolerable nausea/vomiting requiring treatment) (14).

8 ADVERSE EVENT REPORTING

Adverse Event Definition

An adverse event (AE) is any untoward medical occurrence in a subject participating in an investigational study or protocol regardless of causality assessment. An adverse event can be an unfavorable and unintended sign (including an abnormal laboratory and vital sign findings), symptom, syndrome or disease associated with or occurring during the use of an investigational product whether or not considered related to the investigational product.

These events may be:

- a. *Definitely related*: clearly associated with study drug/treatment
- b. *Probably related*: likely associated with study drug/treatment
- c. *Possibly related*: may be associated with study drug or other treatment
- d. *Unlikely to be related*, or
- e. *Definitely not related* to the study drug/treatment

For reporting purposes, an AE should be regarded as definitely or probably related to the regimen if the investigator believes that at least one of following criteria are met:

- a. There is a clinically plausible time sequence between onset of the AE and the administration of the study drug or treatment.
- b. There is a biologically plausible mechanism for the study drug or treatment causing or contributing to the AE.
- c. The AE cannot be attributed solely to concurrent/underlying illness, other drugs, or procedures.
- d. A potential alternative cause does not exist.

Serious Adverse Events (SAE): An adverse drug experience occurring at any dose that results in any of the following outcomes:

- a. Death
- b. A life-threatening adverse drug experience
- c. Inpatient hospitalization or prolongation of existing hospitalization
- d. A persistent or significant disability &/or incapacity
- e. A congenital anomaly or birth defect

Important medical events that may not result in death, be life-threatening, or require hospitalization may be considered a serious adverse drug experience when, based upon appropriate medical judgment, they may jeopardize the patient or subject and may require medical or surgical intervention to prevent one of the outcomes listed in this definition. A serious adverse experience includes any experience that is fatal or immediately life threatening, results in a persistent or significant disability/incapacity, requires or prolongs in-patient hospitalization, or is a congenital anomaly, cancer, or overdose.

Other important medical events that may not result in death, not be life-threatening, or not require hospitalization may be considered a serious adverse experience when, based upon appropriate medical judgment, the event may jeopardize the subject/patient and may require medical or surgical intervention to prevent one of the outcomes listed previously.

Expected adverse events are those adverse events that are listed in the protocol, the Investigator's Brochure (current edition) or in the study informed consent document.

Unexpected adverse events are those that:

- a. are not described in the labeling for Ondansetron
- b. are not anticipated in the study informed consent. This includes adverse events for which the specificity or severity is not consistent with the description in the informed consent.

Unanticipated problem: Per FDA Procedural Guidance for Clinical Investigators, Sponsors, and IRBs (January 2009), A serious problem that has implications for the conduct of the study (requiring a significant and usually safety-related, change in the protocol such as revising inclusion/exclusion criteria or including a new monitoring requirement, informed consent or investigator's brochure).

Unanticipated problem Reporting: Per 21 CFR 312.66, 312.53 (c)(1)(vii), and 56.108(b)(1), should an Unanticipated problem occur during the investigation, the investigator will promptly report all unanticipated problems involving risks to human subjects or others to IRBMED.

The severity or grade of an adverse event may be measured using the following definitions:

Mild: Noticeable to the subject, but does not interfere with subject's expected daily activities, usually does not require additional therapy or intervention, dose reduction, or discontinuation of the study.

Moderate: Interferes with the subject's expected daily activities, may require some additional therapy or intervention but does not require discontinuation of the study.

Severe: Extremely limits the subject's daily activities and may require discontinuation of study therapy, and/or additional treatment or intervention to resolve.

Event reporting: The study will comply with the IRB reporting requirements and guidelines.

All AEs will be recorded by the Investigator from the time the subject signs informed consent until hospital discharge. AEs and serious adverse events (SAEs) will be recorded in the subject's source documents. All SAEs must be reported to the IRB according to the University of Michigan IRB reporting requirements.

9 DATA ANALYSIS/STATISTICAL METHODS

9.1 Sample Size Determination

Anticipating study drug to result in 50% decrease in pruritus from current rate of pruritus for those patients receiving ITM, we need to enroll 56 patients per group to achieve 80% power.

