1 INTRODUCTION

1.1 Indication

Pruritus is one of the most common and bothersome side effects of intrathecal morphine (ITM) in children, with a reported incidence of 30-70% (1, 2, 13, and 15). We previously found a 40% incidence of pruritus in young children who received intrathecal morphine for major urologic surgery (2) (retrospective review, n= 77, anti-pruritic treatment required in 31 cases). Clinicians, who have witnessed unbearable itching and scratching in their young patients after intrathecal morphine, may be reluctant to offer this effective pain control to future patients, for fear of these unpleasant sequelae.

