1.4 Previous Human Experience

5HT3 antagonists are considered among the first line of treatments for morphine-induced nausea as well as pruritus in adult, particularly obstetric, populations (4, 7, 8, 19). A review of placebo RCTs, using prophylactic 5HT3 antagonists for pruritus in neuraxial opioids, found NNTT = 7 to reduce pruritus in adults (29). 5HT3 antagonists block the effects of morphine in animal studies (3). There is a high density of 5HT3 receptors in the nucleus of the facial and trigeminal nerve (20, 25). An “itch center” has been proposed at the spinal tract nucleus of the trigeminal nerve (18). More specifically, pre-emptive (27, 28) and around-the-clock ondansetron (28) dosing with ondansetron has been shown to reduce itch (both incidence and intensity), in adults who received intrathecal opioids.

In the pediatric population, case reports (9-11) suggest ondansetron is an effective treatment for pruritus, but to date there are no data to support the efficacy of 5HT3 antagonists in preventing or treating ITM-related pruritus in children.

In contrast, antihistamines such as diphenhydramine, while used in many pediatric settings, have been shown to be ineffective on opioid-related pruritus, in recent reviews (1, 13). This is corroborated by research in primates (23).

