9.2 Data Analysis

Data will be summarized using descriptive methods. Parametric data will be analyzed between groups using unpaired t tests or Mann Whitney U, as appropriate. Rankings of pruritus and PONV will be coded as none-mild vs. severe and Chi-squared and Fishers' Exact tests will be used to compare these outcomes between groups. Significance will be accepted at the 5% level.

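### Section 9.1 claims 80% power for an unsourced halving from an unstated rate; at the site's own 40% rate, 56 per group gives about 65%, and less if the effect is nearer the cited adult NNT

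*Combined protocol and SAP*

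**What the plan says.** Section 9.1 gives the whole justification in one sentence. Its premise is "Anticipating study drug to result in 50% decrease in pruritus from current rate of pruritus for those patients receiving ITM". The conclusion it draws from that premise is "we need to enroll 56 patients per group to achieve 80% power". It puts no number on the current rate, cites no source for the 50%, and does not say whether the test is one- or two-sided.

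The figures that could fill those gaps are elsewhere:

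- **Control rate (Section 1.1).** Pruritus in children is described "with a reported incidence of 30-70" per cent. The site's own series is more specific: "We previously found a 40% incidence of pruritus in young children who received intrathecal morphine for major urologic surgery" (31 of 77 needed anti-pruritic treatment).
- **Effect (Section 1.4).** A review of placebo-controlled trials of prophylactic 5HT3 antagonists "found NNTT = 7 to reduce pruritus in adults". The control rate behind that NNT is not given. For children, the section says that "to date there are no data to support the efficacy of 5HT3 antagonists in preventing or treating ITM-related pruritus in children".
- **Numbers (Section 3).** 130 children are to be recruited, with 56 in each group.
- **Analysis (Section 9.2).** Pruritus is split into severe versus none or mild and compared by chi-squared and Fisher's exact tests. "Significance will be accepted at the 5% level". Descriptive summaries are planned, but no effect measure or confidence interval is named.

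**The concern.** A stated power can be checked only if the control rate and the effect are both given and supported. Here the control rate is missing and the effect is unsupported. The one site-specific rate in the document does not lead to 56 per group, and the one numeric effect in the document may be smaller than a halving.

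This matters for how the result will be read. By the plan's own account there are no prior efficacy data in children. If true power is well below 80%, a p-value above 0.05 is a likely outcome even when the drug works. Reported without an interval, it could be taken to show that ondansetron does not prevent this pruritus in children.

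**Working it through.** **Inputs.** n = 56 per group (9.1), or 130/2 = 65 if all recruits are analysed (3). Alpha is 5% (9.2), taken as two-sided because sidedness is not stated. Control rate is 40% (31/77 = 40.3%), with a cited range of 30–70% (1.1). Effect is a 50% relative reduction (9.1), or NNT 7 (1.4).

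**Step 1: reproduce 56 per group.** With control rate p1, treated rate p2 and mean m:

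n = [1.96·√(2m(1−m)) + 0.8416·√(p1(1−p1) + p2(1−p2))]² / (p1−p2)²

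- 40% vs 20%: [1.96·√0.42 + 0.8416·√0.40]² / 0.04 = (1.270 + 0.532)² / 0.04 = 81.2, so 82 per group.
- 50% vs 25%: [1.96·√0.46875 + 0.8416·√0.4375]² / 0.0625 = 57.7, so 58 per group.
- 51% vs 25.5%: 56 per group.

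At 40%, other conventions do not give 56 either: 91 with continuity correction, 79 with unpooled variance, 81 by arcsine, 64 one-sided. The figure of 56 matches an unstated control rate of about 51% (two-sided) or 44% (one-sided).

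**Step 2: power for the planned halving.** For 40% vs 20% with 56 per group, the normal approximation gives z = (0.20·√56 − 1.96·√0.42)/√0.40 = 0.36, or 64%. Exact enumeration of the uncorrected two-sided chi-squared test gives:

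| Control rate | 56 per group | 65 per group |
|---|---|---|
| 30% | 49% | 54% |
| 40% | 65% | 72% |
| 50% | 79% | 85% |
| 60% | 90% | 93% |
| 70% | 97% | 98% |

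A one-sided test at 40% with 56 per group would have about 75%.

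**Step 3: sensitivity to the NNT, absolute effect constant.** 1/7 = 14.3 points. This equals a halving only where 0.5·p = 1/7, that is p = 28.6%. Exact chi-squared power for p2 = p1 − 1/7:

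| Control rate | Relative reduction | 56 per group | 65 per group |
|---|---|---|---|
| 30% | 48% | 44% | 50% |
| 40% | 36% | 37% | 42% |
| 50% | 29% | 32% | 37% |
| 60% | 24% | 32% | 36% |
| 70% | 20% | 35% | 40% |

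Fisher's exact test is lower: 36, 30 and 28% at control rates of 30, 40 and 70% with 56 per group.

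**Step 4: the same, relative effect constant.** The relative reduction is (1/7) divided by the adult control rate, which is unknown. Applied to a 40% paediatric rate with 56 per group:

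| Assumed adult control rate | Relative reduction | Power |
|---|---|---|
| 30% | 48% | 60% |
| 40% | 36% | 37% |
| 50% | 29% | 25% |
| 70% | 20% | 15% |

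**Step 5: what a zero difference would show.** The 95% half-width with equal rates is 1.96·√(2p(1−p)/56).

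- At 40%: 1.96·√(0.48/56) = 18.1 points. This excludes the planned 20-point reduction but not 14.3 points.
- At 70%: 17.0 points. This excludes the planned 35 points but not 14.3.
- At 30%: 17.0 points. This excludes neither the planned 15 points nor 14.3.

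**The case against.** A reader might infer that the NNT of 7 proves an effect smaller than a halving at every pruritus rate the plan cites. The documents do not support that. The NNT is from adults and the 30–70% range is for children. An NNT fixes a relative effect only at its own control rate, which is not given; an adult rate below 28.6% would mean more than a halving. If the relative effect carried over from an adult rate of 30% to a paediatric rate of 70%, power would be about 95%.

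Three further points stand. The NNT is for 5HT3 antagonists as a class and for pruritus, while the analysis is of severe pruritus. Section 1.4 also cites adult studies of pre-emptive and around-the-clock ondansetron, closer to this regimen, but without figures, so they cannot settle the size either way. And sizing on a target effect is a legitimate choice; nothing in the plan promises power for an NNT of 7.

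A reader might also infer that a null result would be uninformative. Step 5 shows otherwise: at 40% or 70% it would rule out the planned halving.

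None of this rescues the stated power at the site's own rate. Step 2 grants the full 50% reduction and still finds 65%, so at 40% part of the shortfall comes from the unstated control rate and not from the effect. At 30% nearly all of it does: power is 49% for the halving and 44% for the NNT effect.

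**Conclusion.** The concern holds in a limited form. With 56 per group and a two-sided 5% test, 80% power for a halving requires a control rate of about 50% or higher. The plan neither states nor supports such a rate for the severe-pruritus outcome. At its only site rate, 40%, which is tied to needing treatment, power is about 65% (72% with 65 per group).

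The 50% is unsourced. Power for an effect suggested by the adult NNT is conditional: about 32–44% if the absolute reduction carries over to children and to severe pruritus, or about 15–60% at a 40% rate if the relative reduction carries over from adult control rates of 70% down to 30%. These are sensitivity figures, not estimates of the trial's true power.

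Because Section 9.2 names no interval, the plan as written would not show readers which effects a non-significant result has and has not excluded.

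**What to change.** **Section 9.1.** State the control rate, the outcome it refers to (severe pruritus) and whether the test is two-sided. Give the basis for the 50%. Restate power along these lines: with 56 per group, about 65% for 40% versus 20%, and about 80% or more only for a halving from a control rate of about 50% or higher. Add the NNT figures from steps 3 and 4 as a labelled sensitivity case, with the carry-over assumption written beside them.

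**Section 9.2.** Make the risk difference in severe pruritus, with its 95% CI, the reported primary result beside the chi-squared test. Say that a non-significant result will be interpreted from that interval. Do not add a fixed rule that the interval must exclude 14 points before absence of benefit is discussed: with a half-width near 18 points, that would need ondansetron to do about 4 points worse than placebo (18.1 − 14.3 = 3.8).

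**Cost.** Wording in two sections and a less favourable stated power. No extra patients and no change to treatment or data collection.

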7 ASSESSMENTS

7.1 Primary Endpoint Assessments

For the first 24 hours, subjects will be visited in the PACU, the evening of surgery, the next morning and at 24+/-3 hours (not between the hours of 10p-7a) to obtain the presence and degree of adverse effects, our primary outcomes. Pruritus will be scored similar to previous pediatric studies, as 0 = none; 1 = mild/tolerable/not requiring treatment; 2 = severe/intolerable/requiring treatment (12).

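### Section 9.1 claims 80% power at 56 per group without giving a control rate; at the protocol's own 40% rate, two-sided chi-squared power is about 64–65%

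*Combined protocol and SAP*

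**What the plan says.** The sample size justification in Section 9.1 is one sentence. It anticipates a "50% decrease in pruritus from current rate of pruritus for those patients receiving ITM" and concludes that "we need to enroll 56 patients per group to achieve 80% power". It gives no numerical control rate, treated rate, test, significance level or sidedness.

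The related information is elsewhere in the document:

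- **Rates (Section 1.1).** The literature is summarised "with a reported incidence of 30-70"%. The team's own data follow: "We previously found a 40% incidence of pruritus in young children who received intrathecal morphine for major urologic surgery", from a retrospective review of 77 children with "anti-pruritic treatment required in 31 cases".
- **Outcome (Section 7.1).** Pruritus is scored 0, 1 or 2, the top score being "2 = severe/intolerable/requiring treatment".
- **Analysis (Section 9.2).** "Rankings of pruritus and PONV will be coded as none-mild vs. severe", compared by chi-squared and Fisher's exact tests. "Significance will be accepted at the 5% level". Sidedness is not stated anywhere.
- **Numbers (Section 3).** 130 children are to be recruited, with 56 in each group. No loss allowance is given.

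**The concern.** When the effect is a relative reduction, power depends strongly on the control rate. Halving 30% and halving 70% are very different targets. A claim of 80% power to halve an unspecified rate therefore cannot be checked.

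The natural candidate is the team's own 40%. It counts children who needed treatment, which is close to the score-2 category that Section 9.2 compares. At that rate 56 per group falls well short of 80%. A true halving of severe pruritus would be missed about 35–36% of the time (43% with Fisher's exact test), not 20%, and a null result could be over-read as evidence that ondansetron does not work in children.

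**Working it through.** **Inputs.** Control rate p₁ = 0.40 (Section 1.1; 31/77 = 0.403). Treated rate p₂ = 0.20 (the halving in Section 9.1). n = 56 per group (Sections 3 and 9.1). Significance level 5% (Section 9.2). Two-sided testing is assumed because the document is silent, and one-sided results are shown as well.

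**1. Can the plan's 56 be reproduced?** The pooled formula is

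n = [z_α √(2p̄(1−p̄)) + z_β √(p₁(1−p₁)+p₂(1−p₂))]² / (p₁−p₂)², with p̄ = (p₁+p₂)/2.

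At 40% versus 20%, p̄ = 0.30, 2p̄(1−p̄) = 0.42 and p₁(1−p₁)+p₂(1−p₂) = 0.24 + 0.16 = 0.40. So

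n = (1.960×√0.42 + 0.842×√0.40)² / 0.04 = (1.270 + 0.532)² / 0.04 = 81.2, i.e. **82 per group**.

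| Formula, 40% vs 20%, 80% power | Two-sided n | One-sided n |
|---|---|---|
| Pooled | 82 | 64 |
| Unpooled | 79 | 62 |
| Arcsine | 81 | 64 |
| Continuity-corrected | 91 | 74 |

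None gives 56.

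**2. Which control rate does give 56?** Solving for the rate at which 56 per group has 80% power to detect a halving:

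- Two-sided: 50.9% (pooled), 49.4% (unpooled), 50.7% (arcsine), 51.0% (exact chi-squared).
- One-sided: 43.7%, 42.7%, 43.5% and 44.0% respectively.
- The continuity-corrected formula puts the rate higher, at 55.1% two-sided and 48.2% one-sided.

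At exactly 50% versus 25%, two-sided, n is 55 (unpooled) to 58 (pooled). Power at 56 is then 78.8% (pooled), 80.7% (unpooled), 78.9% (exact chi-squared) or 73.2% (Fisher's exact).

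**3. Power at 56 per group, 40% versus 20%.**

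Power = Φ{[(p₁−p₂)√n − z_α √(2p̄(1−p̄))] / √(p₁(1−p₁)+p₂(1−p₂))}

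= Φ{(0.20×√56 − 1.270) / √0.40} = Φ{(1.497 − 1.270)/0.632} = Φ(0.358) = **0.640**.

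| Method | 56 per group | 65 per group (all 130 analysed) |
|---|---|---|
| Pooled normal, two-sided | 64.0% | 70.6% |
| Exact power of chi-squared, two-sided | 64.9% | 71.6% |
| Fisher's exact, two-sided | 57.3% | 64.1% |
| Pooled normal, one-sided | 75.2% | 80.6% |

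The arcsine and unpooled approximations at 56, two-sided, give 64.8% and 65.8%. Using 31/77 instead of 0.40 gives 64.4% (pooled) and 65.3% (exact chi-squared). The 40% rate reaches 80% in this table only with a one-sided test and no losses at 65 per group, which is not the stated design.

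**4. How firm is 40%?** The 95% Wilson interval for 31/77 is 30.0% to 51.4%. Pooled two-sided power at 56 for a halving is 47.6% at the lower limit and 80.7% at the upper. The 49–51% that 56 requires lies near the top of that interval.

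**5. Detectable effect.** From 40%, 56 per group has 80% two-sided power against a treated rate of 16.4% (pooled), 16.6% (exact chi-squared) or 16.9% (unpooled). That is a relative reduction of about 59% (1 − 16.4/40), not 50%.

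**6. Recruitment.** 2 × 56 = 112, and 1 − 112/130 = 13.8%. The two totals imply a loss allowance of about 14%, which is not stated.

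**The case against.** The strongest reply is that no arithmetic slip is proven. A control rate near 50% reproduces 56 well, it is the midpoint of the 30–70% range in Section 1.1, and it lies inside the interval for the team's own data. The document does not say that 40% was the input. The earlier cohort was retrospective and limited to young children having urologic surgery, whereas the trial takes ages 3–17 for any procedure needing intrathecal morphine and scores pruritus at blinded visits. Section 9.1 also speaks of pruritus generally. If it was sized on any pruritus, the relevant rate could exceed the 40% who needed treatment. Finally, the tests and the 5% level appear in Section 9.2, and two-sided is the ordinary reading.

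Much of this stands. The test and level are missing only from Section 9.1, the 40% is an imperfect match, and a rate near 50% cannot be excluded. None of it rescues the claim as written. No section says 50% was assumed. The 30–70% range is not restricted to pruritus needing treatment, while the only group comparison of pruritus in Section 9.2 counts severe cases. If the range includes mild itch, its midpoint overstates the event rate for that test. Either the rate was 40% and the stated power is wrong, or a higher rate was used without being stated or justified.

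**Conclusion.** The concern holds and should be corrected. Section 9.1 omits the input that determines its power, and at the only single rate the document reports the design does not deliver 80%. The shortfall is about 15–16 percentage points with a two-sided chi-squared test, about 23 with Fisher's exact test and about 5 with a one-sided test.

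This rests on 40% as the control rate for severe pruritus, a true halving, a 5% level and 56 analysed per group. The arithmetic at 40% and the absence of the inputs are certain. Which rate the sponsor used is not known, and the conclusion does not depend on it.

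**What to change.** In Section 9.1, state the control rate, the ondansetron rate, the sidedness and the test on which the calculation rests. Then:

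- **If the rate is 40%:** restate two-sided chi-squared power as about 64–65% at 56 analysed per group (about 71% at 65), and give the effect detectable with 80% power, 40% down to about 16%.
- **If a rate near 50% was assumed:** say so, justify it for severe pruritus against the team's own 31/77, and report power at 40% beside it.
- **In either case:** state the loss allowance that links 130 recruited to 56 per group (about 14%).

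The cost is a wording change in one section, with no extra patients and no change to the analysis. The one drawback for the sponsor is a less favourable stated power if 40% is the rate.
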